## 5.2. Interim Analysis

The Data and Safety Monitoring Board meets monthly; however, a formal interim analyses for overwhelming efficacy is planned after 50% of recruitment is completed (n=75). For the planned interim analysis, a formal detailed statistical report will be written by [name], Biostatistician including protocol adherence, the primary outcome, and adverse events reported as well as center performance in terms of recruitment, data quality, loss to follow-up and protocol violations.

The main statistical issue relevant to interim analysis is the problem of performing multiple tests of significance on accumulating data. A number of procedures have been developed to handle this situation. For this trial, the group sequential method will be used to control the type I error with the Lan-DeMets spending function and the O’Brien-Fleming type boundary. Assuming that the analysis is conducted at precisely 50%, this implies that the alphas to be used will be 0.003 and 0.049 at the interim and final analyses, respectively. However, this should not preclude the Data and Safety Monitoring Board recommending termination earlier if there is evidence of harm. Pre-specified stopping rules for safety will be developed.

It is recognized that any decision to terminate the study would not be reached solely on statistical grounds but on a number of complex clinical and statistical considerations.

### 1.1. Analysis Plan

A detailed Statistical Analysis Plan will be written before the first subject is enrolled into this study. The following is a summary of the proposed plan. [name] will be responsible for statistical computations.

All statistical analyses will be based upon the total cohort of patients randomized into the trial. Although data on some patients may be missing, all relevant data available from each patient will be employed in the analyses. Patients will be included in the treatment group to which they were randomly assigned regardless of treatment actually received (intention to treat).

#### **Analysis Plan for Aim 1 (MOTOR subjects not exposed to BMZ vs BMZ-exposed subjects in usual care group):**

Umbilical cord blood C-peptide levels will be compared between controls not exposed to BMZ from the MOTOR study and BMZ-exposed subjects prospectively randomized to usual care, using a linear model. We will estimate

the mean difference between groups along with a 95% confidence interval. For this comparison between controls not exposed to BMZ from the MOTOR study and BMZ-exposed subjects prospectively randomized to usual care, we will adjust for the following potential confounding factors: periodontal treatment in the MOTOR trial, gestational age at delivery, maternal BMI on admission, and fetal gender. Unfortunately we will not be able to accurately ascertain who among the women prospectively enrolled in the randomized trial has periodontal disease, and thus we will not be able to adjust for periodontitis in our analysis. Periodontitis as an unmeasured confounder is unlikely to bias the analysis of our primary outcome, umbilical cord blood C-peptide, but could bias the analysis of other secondary outcomes which are related to inflammation, such as cortisol. We will plan to state this as a limitation of the study in the final manuscript and interpret the results accordingly. A planned subgroup analysis will be performed comparing the BMZ-unexposed controls to women who were randomized to usual care and delivered within 3 days of BMZ exposure. Other 2° outcomes including umbilical cord blood cortisol, insulin-like growth factor, and leptin levels will be tested in similarly. We will not adjust for multiple comparisons, but will present results for all comparisons regardless of “significance.”

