#### 3.3. Design Summary

This proposal includes use a retrospective cohort of 75 mother-neonate dyads and umbilical cord samples collected during the Maternal Oral Therapy to Reduce Obstetric Risk (MOTOR) trial, as well as a prospective cohort of 144 mother-neonate dyads prospectively enrolled in our randomized clinical trial.

Women who had enrolled in the MOTOR trial, now completed, will serve as unexposed controls for this new proposal, as antenatal BMZ was reserved for threatened PTB less than 34 weeks' gestation at the time the trial was conducted. The MOTOR trial was a randomized, blinded trial of 1,760 pregnant women with periodontal disease to measure the impact of periodontal treatment during pregnancy on maternal and neonatal outcomes. Of these, there are approximately 1500 stored umbilical cord blood specimens from otherwise healthy, non-diabetic women, 5% of whom delivered between 34 weeks 0 days and 36 weeks 6 days. We have

been granted access to use 75 umbilical cord blood samples which meet inclusion criteria as unexposed late PTB controls to compare to the samples we collect in our randomized clinical trial.

For this randomized clinical trial, we will enroll 144 non-diabetic women with singleton pregnancies who are receiving betamethasone between 34 weeks 0 days and 36 weeks 5 days in anticipation of late preterm delivery. Eligible, consenting women will be randomized to one of two management schemes:

1. Intervention group: maternal capillary blood glucose (CBG) screening with treatment of hyperglycemia with insulin per existing institution protocol for diabetic women. Guidelines based on the existing UNC-CH algorithm for treatment of diabetic women are demonstrated Tables 1 and 2 below.

Table 5 Maternal insulin algorithm if NPO	
CBG q 1-2hr	IV Regular Insulin
<110mg/dL	Stop insulin infusion
111-140mg/dL	1 U/hr
141-180mg/dL	1.5 U/hr
181-220mg/dL	2 U/hr
>220mg/dL	2.5 U/hr & titrate

Table 6 Maternal insulin sliding scale if eating general diet	
CBG fasting and 1hr post-prandial	SQ Insulin
<110 mg/dL	0 units
111-140 mg/dL	1 unit if fasting BG*
141-180 mg/dL	1 unit
181-220 mg/dL	2 units
>220 mg/dL	4 units & consider infusion

2. Control group: usual care with no CBG screening or treatment as is current protocol at UNC-CH as well as other participating institutions

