### 4.4. Patient Management and Follow-up

Other than the timing and frequency of maternal glucose screening and recommended thresholds for treatment of hyperglycemia detailed in the study protocol, women will receive standard care as defined by their clinical provider. Women randomized to the intervention arm will undergo screening for and treatment of maternal hyperglycemia until delivery or hospital discharge for a maximum of 5 days following BMZ.

All study neonates will have CBG testing within 2 hours of life. This is standard of care for neonates born at less than 37 weeks. As part of the study protocol, CBG will be measured within 2 hours of life on those neonates who are delivered at or after 37 weeks and 0 days. The remainder of neonatal care will be according to the clinical provider. Umbilical cord blood and placental samples will be collected after delivery to evaluate fetal metabolic status in utero as well as other genetic changes. All study specimens will be labeled with a unique study ID code. Personnel responsible for lab assays will receive the specimens in a coded fashion without any documentation of PHI or study arm.

- Placental biopsies:
  - 15 punch biopsies will be obtained from each placenta using a standard 3mm punch biopsy tool. Biopsies should be obtained 2 cm from the cord insertion site.
  - Three punch biopsy samples will be placed into 5 separate aliquot tubes.
  - 0.5mL AllProtect solution will be placed in 3 of the 5 aliquot tubes
  - The other 2 aliquot tubes will be empty
- Placental portions:
  - 2 placental portions should be removed using sharp dissection (scalpel or scissors). Each portion should measure approximately 0.5 by 0.5 inches and should traverse the complete depth of the placenta.
  - Each placental portion should be placed into a 15mL falcon tube
  - The distance from the cord insertion should be recorded. One portion should be removed 2 cm from the cord insertion. The other should be removed 2 cm from the periphery.

While maternal CBG will only be performed for maximum of 5 days following BMZ, maternal postpartum data will be collected through hospital discharge. Neonatal data will be collected through hospital discharge or until 28 days of life.

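### Aim 1 sets controls chosen for birth at 34w0d–36w6d against all usual-care births, so any usual-care birth at or after 37w0d has no control of the same gestation

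*Combined protocol and SAP*

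**What the plan says.** **Controls.** Section 3.3 (Design Summary) describes about 1500 stored MOTOR cord specimens, "5% of whom delivered between 34 weeks 0 days and 36 weeks 6 days". The investigators have "been granted access to use 75 umbilical cord blood samples which meet inclusion criteria as unexposed late PTB controls". The controls are therefore selected on actual gestation at birth.

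**Trial women.** Section 3.4.1 selects on gestation at first betamethasone dose (34w0d–36w5d) and on delivery expected within 12 hours to 7 days. Scheduled inductions must start by 36w5d, scheduled cesareans must take place by 36w6d, and inpatient care until delivery must be planned. Section 3.4.3 excludes delivery planned for 37w0d or later. No rule concerns the gestation at which birth actually occurs.

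**Later births are foreseen.** Section 4.4 makes glucose testing a study procedure for "those neonates who are delivered at or after 37 weeks and 0 days". In the intervention arm, screening runs "until delivery or hospital discharge for a maximum of 5 days following BMZ", which suggests that discharge before delivery was also contemplated.

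**Analysis.** The general Analysis Plan states: "All statistical analyses will be based upon the total cohort of patients randomized into the trial". The Aim 1 plan compares "controls not exposed to BMZ from the MOTOR study and BMZ-exposed subjects prospectively randomized to usual care, using a linear model", and removes no usual-care birth by gestation. It will "adjust for the following potential confounding factors: periodontal treatment in the MOTOR trial, gestational age at delivery, maternal BMI on admission, and fetal gender", and it adds a subgroup "comparing the BMZ-unexposed controls to women who were randomized to usual care and delivered within 3 days of BMZ exposure".

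**The concern.** The two groups enter Aim 1 under different rules. One is defined by when birth happened, the other by when betamethasone was given and when delivery was planned. The rules agree for most women but not for a usual-care woman who gives birth at or after 37w0d: no control was born then.

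A covariate for gestational age at delivery does not supply the missing comparator. At those gestations the model carries forward the trend seen before 37w0d, and the control data cannot show whether that is right. If the betamethasone effect in those births differs, or the trend bends, the Aim 1 estimate moves by an amount the data cannot reveal.

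Aim 1 is one of two primary research questions and is not a randomized comparison, so comparability of the groups rests on selection and the model.

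**Working it through.** **1. Can such births occur?** A first dose at 36w5d followed by birth 2 days later gives 37w0d; 3 days gives 37w1d; 7 days gives 37w5d. The limits on planned delivery mean that only unplanned prolongation gets there. Births before 34w0d cannot occur, because the first dose is at 34w0d or later. The mismatch is at the upper end only.

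**2. The plan's own figures.**
- Controls: 1500 × 5% = 75, the number granted.
- Usual care after 10% loss (section 5.1): 0.9 × 72 ≈ 65.
- Delivering after 3 days: 65 − 50 = 15 (23%).
- Stated Aim 1 power of at least 80%: a simple two-group comparison of 75 with 65, two-sided 0.05, gives 97.6%, 97.6%, 94.3% and 99.3% for the four Table 4 rows. The claim is reproduced.

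**3. Shift in the estimate.** The documents give no count of term births, so k = 3, 6 or 13 of 65 is assumed. Taking 13 would put nearly all of the 15 later deliveries at term, so it is an upper extreme. Let p = k/65, and let r be the effect in term births as a fraction of the effect before 37w0d. With a linear gestational-age term, the fraction of the effect lost is

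(1 − r) × (p − γδ).

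Here δ is the difference in mean gestation (usual care minus controls), W is the pooled within-group sum of squares of gestation, and γ = 65p(1−p)D/W, where D is the gap in mean gestation between term and earlier usual-care births.

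Assumed setting: gestation before 37w0d is uniform over 34–37 weeks in both groups (mean 35.5, variance 0.75), and term births are uniform over 37w0d–37w5d (mean 37.357, variance 0.0425). Then D = 1.857, δ = pD, and W = 75 × 0.75 + 65 × [0.75(1−p) + 0.0425p + p(1−p)D²].

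| k | p | δ (weeks) | W | γ | lost, r = 0 | lost, r = 0.5 | lost, r = 1 |
|---|---|---|---|---|---|---|---|
| 3 | 0.0462 | 0.086 | 112.8 | 0.047 | 4.2% | 2.1% | 0 |
| 6 | 0.0923 | 0.171 | 119.5 | 0.085 | 7.8% | 3.9% | 0 |
| 13 | 0.2000 | 0.371 | 131.7 | 0.147 | 14.6% | 7.3% | 0 |

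Simulations that add BMI and sex, with and without the periodontal-treatment term, and vary the spread of gestation (term births up to 39w0d) give 3.9–4.3%, 6.9–8.1% and 12.1–15.4% for r = 0, and 2.0–2.1%, 3.4–4.0% and 6.0–7.7% for r = 0.5. If usual-care births start slightly later than the controls (34.3 weeks) and term births run to 39w0d, the loss is smaller. For k = 13, r = 0: δ = 0.62, γ = 0.163, and 0.200 − 0.163 × 0.62 = 0.099, about 10%.

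Against sampling error this is modest. In the weakest Table 4 row (1.5/2.5 = 0.6 SD) with k = 6, the shift is 0.6 × 0.039 = 0.023 SD for r = 0.5, or 0.14 of a standard error of 0.170 SD. For r = 0 it is 0.6 × 0.078 = 0.047 SD, or 0.27 of a standard error.

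**4. Cost of restriction.** In the same setting the standard error in SD units is √(1/75 + 1/65 + δ²/W) for all births and √(1/75 + 1/(65−k)) after restriction.

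| k | all births | restricted | rise |
|---|---|---|---|
| 3 | 0.1697 | 0.1716 | 1.2% |
| 6 | 0.1702 | 0.1740 | 2.2% |
| 13 | 0.1725 | 0.1805 | 4.6% |

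Across the simulated settings the rise is 0.8–1.3%, 1.5–2.4% and 2.9–5.1%.

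**5. What restriction leaves untouched.** Suppose instead that all 15 later deliveries have half the effect, whatever their gestation. Ignoring covariates, the all-births estimate is 0.6 × (1 − 0.5 × 15/65) = 0.531. Removing 3 term births gives 0.6 × (1 − 0.5 × 12/62) = 0.542; removing 6 gives 0.6 × (1 − 0.5 × 9/59) = 0.554. Most of that dilution remains.

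**The case against.** The strongest reply is that the documents give no reason to expect a weaker effect because of gestation itself. Section 2.3 says maternal hyperglycemia lasts 3–4 days for most women, which concerns time since betamethasone. A birth at 37w0d soon after dosing is inside that period; a birth at 35w5d twelve days after dosing is outside it and would stay in a restricted analysis. The plan already addresses interval through the within-3-days subgroup and the time-since-dose models. With an equal effect and a linear trend there is no bias, and no departure from linearity has been shown. Restriction also selects on something that happens after exposure and departs from the total-cohort wording.

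Much of this stands, and it rules out four readings that a reader might infer:

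- *That term births dilute Aim 1 because hyperglycemia has worn off, and that restriction cures this.* Step 5 shows that it mostly would not.
- *That the within-3-days subgroup is diluted too.* It can include births up to 37w1d, but those women are inside the period in section 2.3, so the documents give no ground for a reduced effect there.
- *That usual-care gestation is unlimited.* Planned delivery is capped before 37w0d; only actual birth is not.
- *That the stated Aim 1 power is wrong.* It is reproduced.

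The lack of overlap itself is not answered. The selection rules differ, term births are foreseen and retained, and no control exists at those gestations. Selecting on gestation at birth is how the controls were already chosen, and Aim 1 has no randomization to break.

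**Conclusion.** The point holds as a lack of overlap in gestation at birth, of small and unknown size. The mismatch is read directly from the text; its consequence depends on assumptions. With 3 or 6 assumed term births among 65, the adjusted estimate loses about 2% or 4% at half effect and about 4% or 8% at no effect; with 13, about 7% or 14%. It loses nothing if the effect is equal and the trend linear. Neither the number of term births nor their effect can be learned from the documents. The change is worth making because it is cheap and lets the main estimate rest on gestations that both groups share, not because a material bias has been shown. Confidence is medium.

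**What to change.** In the detailed SAP that the protocol says is to be written:

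- Limit the main Aim 1 comparison to usual-care births at 34w0d–36w6d, the window used to select the controls.
- Apply the same limit to the within-3-days subgroup, for consistency only.
- Report the analysis of all usual-care births alongside, with the number born at or after 37w0d.
- State that this is an exception, for Aim 1 only, to the total-cohort rule, and that interval since betamethasone is handled by the planned subgroup and time-since-dose models.

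**Cost.** Wording only; no new data. A few usual-care women leave the main Aim 1 set, which is then selected on gestation at birth in both groups. The standard error rises by about 1%, 2% or 3–5% for 3, 6 or 13 term births. In the weakest Table 4 row, with all planned covariates and half the controls assumed to have had periodontal treatment, power with an equal effect goes from 82%, 82% and 81% to 82%, 81% and 79%. With half the effect in term births, it goes from 81%, 79% and 75–76% to 82%, 81% and 79%. Aim 2 is unchanged.

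### Does adjusting Aim 1 for periodontal treatment, but not for periodontitis, make the cortisol comparison more biased?

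*Combined protocol and SAP*

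**What the plan says.** Section 3.3 (Design Summary) describes the source of the controls: "The MOTOR trial was a randomized, blinded trial of 1,760 pregnant women with periodontal disease to measure the impact of periodontal treatment during pregnancy". From it the trial takes "75 umbilical cord blood samples which meet inclusion criteria as unexposed late PTB controls". Every control therefore had periodontal disease, and some were treated for it during pregnancy. The treated share among the 75 is not given.

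The Analysis Plan for Aim 1 compares these controls with betamethasone-exposed women randomised to usual care, using a linear model: "we will adjust for the following potential confounding factors: periodontal treatment in the MOTOR trial", with gestational age at delivery, maternal BMI and fetal sex. Because the disease cannot be accurately ascertained in the trial women, "we will not be able to adjust for periodontitis in our analysis". The plan then weighs the consequence. For C-peptide, "Periodontitis as an unmeasured confounder is unlikely to bias the analysis of our primary outcome". For others, it "could bias the analysis of other secondary outcomes which are related to inflammation, such as cortisol". It undertakes to state this as a limitation in the manuscript and to read the results in that light. Cortisol goes through the same model: "Other 2° outcomes including umbilical cord blood cortisol, insulin-like growth factor, and leptin levels will be tested in similarly".

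The coding of the treatment covariate for trial women is not stated. The introduction to the Analysis Plan promises a detailed SAP before the first enrolment and says of the present text: "The following is a summary of the proposed plan".

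**The concern.** No trial woman was treated in MOTOR, so the natural code for all of them is 0 and the covariate varies only among controls. The betamethasone coefficient then compares usual care with the controls not treated in MOTOR, the group expected to carry the full effect of the disease. Treated controls inform only the treatment term, the other slopes and the residual variance.

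A reader who sees periodontal treatment among the adjusted confounders might take it as partial protection against periodontal confounding. For cortisol it could do the opposite: part of a difference credited to betamethasone might be the difference between women with untreated periodontal disease and women mostly without it. The planned limitation mentions unmeasured periodontitis, but not that this covariate can alter the size of the resulting bias, nor which controls the estimate refers to.

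**Working it through.** **Inputs from the documents.** 75 controls (section 3.3); 72 usual-care women, about 65 after 10% loss (72 × 0.9 = 64.8) and 50 delivering within 3 days (section 5.1); Table 4 differences and SDs of 0.5/0.75, 1/1.5, 1.5/2.5 and 1.5/2, that is 0.667, 0.667, 0.6 and 0.75 SD.

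**Assumptions, none in the documents.** Two-sided 5% tests; 38 controls untreated and 37 treated in MOTOR (share treated s = 37/75 = 0.493); P = effect of untreated periodontitis on the analyte, in SD; q = share of trial women with untreated periodontitis; f = fraction of P removed by treatment, acting only through the disease.

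**The plan's own figure.** Section 5.1 states at least 80% power for Aim 1 C-peptide. By normal approximation, 65 v 75 gives 97.6, 97.6, 94.3 and 99.3% over the four Table 4 rows. With only the 38 untreated controls as reference the figures are 90.4, 90.4, 83.6 and 95.7%, so the statement holds either way. The standard error rises from √(1/65 + 1/75) = 0.1695 SD to √(1/65 + 1/38) = 0.2042 SD, a ratio of 1.205. In the 3-day subgroup (50 v 38) the weakest row falls to 79.6%, against 90.8% with all 75.

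**The identity.** Write the mean as a + bG + cT, with G = 1 for trial women and T = 1 for treated controls. Untreated controls have mean a, treated controls a + c, trial women a + b. So b = mean(trial) − mean(untreated controls). In a numerical check the regression and the hand calculation both gave 0.0026; the difference from all 75 controls was 0.0291. This depends on the coding. If T is centred within MOTOR, with trial women at 0, b becomes the contrast with the average control.

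**Bias in b, in units of P.**
- Adjusted, trial women coded 0: q − 1
- Without the treatment term (pooled): q − 1 + fs
- Treated controls as reference: q − 1 + f

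For f > 0 the adjusted bias is larger than the pooled bias only when q < 1 − fs/2: below 0.753 at f = 1 and below 0.877 at f = 0.5. At f = 0 all three are equal.

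| q | f | Adjusted | Pooled | Treated reference |
|---|---|---|---|---|
| 0.25 | 0 | −0.75 | −0.75 | −0.75 |
| 0.25 | 0.5 | −0.75 | −0.50 | −0.25 |
| 0.5 | 0.5 | −0.50 | −0.25 | 0 |
| 1 | 0.5 | 0 | +0.25 | +0.50 |

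**False-positive rates** (6,000 simulated trials per row, 65/38/37, three further covariates, no betamethasone effect).

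| P | q | f | Adjusted | Pooled | Treated reference |
|---|---|---|---|---|---|
| 0.5 | 0.25 | 0.5 | 43% | 31% | 10% |
| 0.3 | 0.25 | 0.5 | 19% | 14% | 6% |
| 0.5 | 0.25 | 0 | 42% | 57% | 42% |
| 0.5 | 0.75 | 0.5 | 9% | 5% | 9% |
| 0.5 | 1 | 0.5 | 5% | 11% | 22% |
| 0 | any | any | 5% | 5% | 5% |

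In the first row the covariate adds about 12 points to a rate that is already 31% without it; in the second it adds about 5. Most of the excess over 5% is the unmeasured periodontitis that the plan discloses. In the third row the bias is the same in all three, and the pooled model rejects more often because its interval is narrower.

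**The case for a change.** The strongest case for a change is that the reference-group point is algebra, that the plan names cortisol as vulnerable and still sends it through a model that can make matters worse, and that the remedy is cheap: state the coding, show cortisol against untreated, pooled and treated controls side by side, and add a clause to the limitation. Not knowing q, on this view, is itself the reason to show all three contrasts.

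Much of this stands. With trial women coded 0 the algebra is right. The plan does not say which controls the estimate refers to, and enlargement covers a wide range of q when treatment works. What does not stand is the step from there to a fault. The coding is open, and the promised detailed SAP is the normal place for it. Trial women did not receive MOTOR treatment, so removing its effect from the controls is a defensible target. The three contrasts change order as q and f change, so none can be called correct, and showing them together leaves the bias where it was. A reader told in the manuscript that periodontitis could bias cortisol has the essential warning, even without the detail of how one covariate scales it.

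**Conclusion.** No change to the plan follows. The covariate choice is a fair trade-off, and its unstated coding is a detail that analysts can settle sensibly in the detailed SAP.

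Only inflammation-related secondary outcomes in the non-randomised Aim 1 comparison are at issue, and the plan names one, cortisol. For these the treatment term may enlarge, leave unchanged or reduce a bias that the plan already discloses. At an assumed P of 0.5 SD and f of 0.5, it moves the false-positive rate from about 31% to 43% at q = 0.25, and from 11% to 5% at q = 1. For C-peptide, on the plan's own judgement that periodontitis is unlikely to matter, the cost is an interval about 20% wider at an assumed even split of treated and untreated controls. Full-arm power stays at 83.6% or more. Aim 2 is randomised and does not use these controls.

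The conclusion rests on trial women being coded 0 and on treatment acting only through the disease. P, q, f and the treated share are unknown, so neither the size nor the direction of the covariate's effect can be fixed from the documents.

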### 3.4. Eligibility Criteria

#### 3.4.1. Inclusion Criteria

1. Singleton Pregnancy. A multiple gestation reduced to singleton (either spontaneously or therapeutically) before 14 weeks 0 days by project gestational age (see Section 3.4.2 below) is acceptable.
2. Gestational age at time of 1st dose of betamethasone administration between 34 weeks 0 days and 36 weeks 5 days confirmed by study criteria (see Section 3.4.2 below)
3. Receiving or already received betamethasone for clinical indications within 6 hours of randomization.
4. Likelihood of delivery in the late preterm period (any one of the following):
  - a. Membrane rupture as defined by visible leakage of amniotic fluid from the cervix, Positive AmniSure test, or the presence of any two of the following:
    - i. Pooling of fluid in the vaginal vault
    - ii. Positive nitrazine test
    - iii. Ferning of vaginal fluid
  - b. Preterm labor with intact membranes. Preterm labor is defined as at least 6 regular uterine contractions in 60 minutes and at least one of the following:
    - i. Cervix greater than or equal to 3cm dilated
    - ii. At least 75% effaced
  - c. Maternal or fetal indication for delivery (either by induction of labor or cesarean section) at less than 37 weeks' gestation (e.g. placenta accreta).
  - d. Delivery expected in no less than 12 hours and no more than 7 days, as deemed necessary by the provider. An induction must be scheduled to start by 36 weeks 5 days at the latest, whereas a cesarean delivery must be scheduled by 36 weeks 6 days at the latest.

5. Planned inpatient management until delivery.

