### 3.4.3. Exclusion Criteria

1. Diabetes, pregestational or gestational
2. Any prior antenatal corticosteroid course during the current pregnancy
3. Systemic corticosteroid administration during pregnancy (at least 5mg oral prednisone or its equivalent for at least 3 weeks)
4. Planned outpatient treatment with antenatal corticosteroids
5. Current multiple gestation or multiple gestation reduced to a singleton gestation at or after 14 weeks 0 days by project gestational age either spontaneously or therapeutically
6. Fetal demise, or known major fetal anomaly, including cardiac anomaly and hydrops
7. Maternal contraindication to insulin: history of hypersensitivity reaction to any components of the medication
8. Delivery planned within 12 hours of randomization
9. Delivery planned at or after 37 weeks 0 days gestation
10. Delivery planned outside the E-ALPS Consortium
11. Participation in another interventional study
12. Participation in this trial in a previous pregnancy

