**Analysis Plan for Aim 2 (BMZ-exposed subjects in usual care group vs intervention group):**

Cord blood C-peptide levels will be compared between randomized arms (usual care vs. screening/treatment after BMZ) using a linear model, controlling for gestational age at randomization. We will estimate the mean difference between groups along with a 95% confidence interval. Similar models will be used to compare 2° metabolic measurements such as cord blood cortisol, insulin-like growth factor, and leptin levels between BMZ-exposed usual care vs. BMZ-exposed intervention group. Metabolic and hormonal analytes will be correlated with our exploratory outcomes: neonatal hypoglycemia (defined as neonatal glucose < 40mg/dL within 48 hours of birth), NICU admission, and NICU stay  $\geq$  72 hours.

If the 2 groups show a difference in the 1° outcome, interactions will be evaluated using linear regression models and subgroup analyses conducted to determine whether the effect differs across particular subgroups of patients. In particular we will assess subgroups defined by gestational age (dichotomized at 36 wks), interval from BMZ exposure to delivery (dichotomized at 3 days), maternal obesity (defined as BMI  $\geq$  30 kg/m^2 at time of delivery), race/ethnicity, and expected indication for late preterm delivery at trial entry (preterm premature rupture of membranes vs. preterm labor vs. obstetrical/medical indication). We will conduct 2° analyses to examine neonatal sex (male vs. female) on the 1° outcome.

We will use linear regression models to assess the association between randomization arm, time since first dose of BMZ until delivery, doses of BMZ received, and the interactions of the latter two with each of the study arm approaches (usual care vs. screening/treatment). We will estimate the association between time interval to delivery and number of BMZ doses separately in each study arm and compare the associations between arms.

Loss to follow-up will be defined as the inability to ascertain whether the neonate was born alive and if born alive umbilical cord blood not collected. Those defined as lost to follow-up will not be included in the primary analysis. It is expected that the loss to follow-up rate will be very low, less than 10 percent. However, a sensitivity analysis will be performed including patients lost to follow-up with “worst case” assumptions regarding their outcome to determine whether the results are robust.

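### The Aim 1 comparison with MOTOR controls does not adjust for reason for delivery, so a difference in case mix may be confounded with the betamethasone association

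*Combined protocol and SAP*

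**What the plan says.** Aim 1 is one of the two primary research questions in section 3.1. The Analysis Plan for Aim 1 compares the MOTOR samples with "BMZ-exposed subjects prospectively randomized to usual care, using a linear model". The adjustment set is "periodontal treatment in the MOTOR trial, gestational age at delivery, maternal BMI on admission, and fetal gender". The only unmeasured confounder discussed there is periodontitis.

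Section 3.3 (Design Summary) describes the source of controls as "approximately 1500 stored umbilical cord blood specimens from otherwise healthy, non-diabetic women, 5% of whom delivered between 34 weeks 0 days" to 36 weeks 6 days, and says the investigators have "been granted access to use 75 umbilical cord blood samples which meet inclusion criteria as unexposed late PTB controls". It does not say which criteria were checked.

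Trial women enter under section 3.4.1, item 4: "Likelihood of delivery in the late preterm period (any one of the following"). The routes are membrane rupture, defined preterm labor, and a maternal or fetal indication. A window of 12 hours to 7 days to expected delivery is listed as a fourth entry, although it reads as a timing condition. Item 5 requires planned inpatient care, and section 3.4.3 excludes "Delivery planned within 12 hours of randomization".

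Reason for delivery is used in one place only. The Analysis Plan for Aim 2 lists "expected indication for late preterm delivery at trial entry", in three classes, as a subgroup factor.

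**The concern.** In a comparison with historical controls, the covariates are the only protection against confounding. Here one group was recruited through a reason for expected delivery, and the other was drawn from women who turned out to deliver late preterm in a periodontal treatment trial. Nothing described makes the balance of ruptured membranes, spontaneous labor and indicated delivery the same in both.

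The plan already treats indication as something that might matter for C-peptide, since it is a subgroup factor in Aim 2. There the arms are randomised and it cannot confound. In Aim 1, where it could, it is neither adjusted for nor named as a limitation. At stake is whether a C-peptide difference between the groups can be attributed to betamethasone. Section 1.1 sets out to define the fetal response to that exposure, so the reading will be causal even though section 3.1 words Aim 1 as an association.

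**Working it through.** **1. The plan's own Aim 1 power figure.** Section 5.1 claims at least 80% power under the Table 4 scenarios.
- Inputs: 75 controls; 72 per arm less 10% loss, 72 × 0.9 ≈ 65; two-sided 0.05 (sidedness is assumed).
- Formula: noncentrality = d × √(n₁n₂/(n₁+n₂)); power ≈ Φ(noncentrality − 1.96).
- Least favourable scenario, d = 1.5/2.5 = 0.6: 0.6 × √(75 × 65/140) = 3.54, power 94%.
- The other scenarios give 97.6% (0.5/0.75 and 1/1.5) and 99.3% (1.5/2).
- Against the 50 women expected to deliver within 3 days, the lowest figure is 91%.

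The claim of at least 80% holds. Power is not the problem.

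**2. What the control count shows.** 1500 × 5% = 75, so the number granted equals the whole estimated late preterm pool and leaves little visible room for a further filter. This is suggestive only. Both inputs are rounded: 4.5% to 5.5% of 1500 is about 68 to 83.

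**3. The two groups side by side.**

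| Feature | Trial women | MOTOR controls |
|---|---|---|
| Gestation | first dose at 34w0d to 36w5d | delivered at 34w0d to 36w6d |
| Health | no diabetes; maternal indications admitted | otherwise healthy, non-diabetic |
| Reason for delivery | entry criterion, item 4 | no selection described |
| Planned inpatient care, expected time to delivery | required | none described |
| Betamethasone (item 3) | required | cannot apply |

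**4. Possible size of the bias.** Bias = (difference in share of an indication) × (C-peptide shift for that indication). The documents give neither factor, so both are assumed.
- Low: 0.20 × 0.3 = 0.06 mcg/L. High: 0.40 × 0.5 = 0.20 mcg/L. The sign is unknown.
- Against the smallest Table 4 difference (0.5): 12% to 40%.
- Against the bolded difference (1): 6% to 20%.
- Against the quoted exposed and normal values (2.85 less 0.6 to 1.0, so 1.85 to 2.25): 0.06/2.25 ≈ 3% to 0.20/1.85 ≈ 11%.

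**5. Effect on the test if betamethasone did nothing.** SE = SD × √(1/75 + 1/65). Rejection rate = Φ(bias/SE − 1.96) + Φ(−bias/SE − 1.96).
- SD 0.75: SE 0.127, rejection 8% to 35%.
- SD 1.5: SE 0.254, rejection 6% to 12%.

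The nominal rate is 5%.

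**6. Precision after adjustment.** A covariate related to group multiplies the variance by 1/(1 − R²), where R² is between group and indication (assumed 0.05 to 0.30). At d = 0.6, normal approximation:

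| Controls v usual care | R² = 0.05 | R² = 0.30 |
|---|---|---|
| 75 v 65 | 93% | 84% |
| 60 v 65 | 90% | 80% (79% by noncentral t) |
| 75 v 50 (3-day subgroup) | 89% | 79% |
| 60 v 50 (3-day subgroup) | 86% | 75% |

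The 60 is illustrative, for the case that some samples fail the criteria.

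**The case against.** The strongest reply is that no imbalance has been shown. The item 4 routes are also the usual ways in which a control would come to deliver late preterm, so different entry rules need not produce a different mix. No section says that C-peptide differs by indication, and listing a factor for Aim 2 subgroups does not make it a confounder in Aim 1. All of this stands. It limits the point to confounding that is possible and uncontrolled.

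A reader might go further and infer that the controls were chosen on gestation at delivery alone, or that a difference in case mix will be reported as a betamethasone effect. The documents support neither. Section 3.3 also restricts controls to otherwise healthy, non-diabetic women and says they meet inclusion criteria. That phrase most naturally means the criteria that can apply to unexposed women, so the betamethasone item is a gap in wording and not evidence of bias. The restriction to healthy women hints at fewer medical indications among controls but gives no mix.

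Two practical objections also stand. The Aim 2 variable is the expected indication at entry, which has no MOTOR counterpart, and the documents do not say whether MOTOR recorded the reason for delivery.

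The analysis section calls itself a summary, with a detailed plan to follow. That does not settle the matter, because the covariates and the one unmeasured confounder are already listed as specific items.

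**Conclusion.** The point holds in limited form. Aim 1 is a primary, non-randomised comparison. No selection or matching of controls on reason for delivery is described, and the model has no term for it, so confounding by delivery indication is uncontrolled and unacknowledged. The documents show that the mix may differ, not that it does.

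The bias of 0.06 to 0.20 mcg/L rests wholly on assumed inputs and could go either way, creating an apparent association or masking a real one. It is modest against the contrast implied by the quoted exposed and normal values, and material only if the true difference is near the low end of Table 4. The plan should be changed on this point. The randomised Aim 2 comparison is unaffected.

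**What to change.** 1. Add actual delivery indication (rupture of membranes, preterm labor, obstetrical or medical indication) to the Aim 1 linear model, coded by the same rules from delivery records in both cohorts. For trial women the Labor and Delivery Summary form is the natural source. Tabulate indication by group first: if a class is nearly empty in one group, the adjusted estimate rests on extrapolation and should be reported as such.
2. If MOTOR did not record indication, name it beside periodontitis as an unmeasured confounder and limit the Aim 1 conclusion accordingly.
3. In section 3.3, state which trial criteria were applied to the MOTOR samples and give the control count as up to 75.

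The cost is abstraction from MOTOR records, 2 degrees of freedom out of about 140, and some precision if indication is strongly imbalanced. In the least favourable scenario, power stays above 80% with all 75 controls against 65. It is only about 80% with 60 controls at R² = 0.30, and can fall below 80% in the 3-day subgroup. An indication term does not remove the differences in planned inpatient care and expected time to delivery, which belong in the limitations either way.
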